5.2. Study procedures

Firstly, this study will start with the assessment of team characteristics, to develop a suited implementation strategy that fits the team and local context but does not influence the fidelity of function. Depending on the composition of the team, education levels and competences in the team, education and training content will be established by a team of coaching experts,

consisting of independent NPs and GPs with extensive experience in PC and PR. The intervention group will be educated in identifying patients with PC needs and will be taught how to apply PR in a four-day training with practical assignments. After two weeks of providing this four-day training to the nursing team, team coaches will be coached by means of a coaching on the job trajectory once a fortnight by the team of expert coaches. Team coaches that will be trained work as NP or SN within one of the organizations and are teamed up with RNs of the general nursing team. The team coaches will perform day to day coaching on the job. The implementation of the intervention will take approximately one month and will be planned in collaboration with the teams and the coaches.

Additionally, nurses who are enrolled in the study will be invited to complete questionnaires individually at enrolment and at six months about their own current symptom management practices, roles and responsibilities, collaboration, communication, and competences.

Secondly, the research team will perform an assessment of baseline measurements in participating patients and request to complete a questionnaire regarding demographic characteristics. The assessment of baseline measurements will be performed by post, mail, telephone, or teleconsulting depending on what is the most suitable and least burdensome for the patient. Subsequently, patients will complete at one-, three- and six-months a questionnaire containing questions regarding symptom control, quality of life and symptom burden. If these questionnaire reveals that a patient does not suffer from any symptoms, it will be excluded from the study. However, the excluded patients will be asked to complete the Lastmeter questionnaire to detect symptoms that may develop at a later stage, to be able to reconsider their inclusion in the study. After each questionnaire and/or assessment patients will be offered support of a NP, specialised in PC to talk about possible thoughts or concerns raised by completing the questionnaires.

Lastly, an assessment of demographic characteristics and perceived care burden on the primary caregiver is performed by the research team. Thereafter, at one-, three- and six-months perceived care burden is evaluated by telephone using the EDIZ rating scale. After each assessment the primary caregiver will be offered support of a NP, specialised in PC to talk about possible thoughts or concerns raised by completing the questionnaires.

Blinding:

In causal studies, blinding is performed ideally at participant, data collection and data analysis level. In this case, however, blinding at the analysis level is the only feasible.

- The participants are not blinded. Patients, primary caregivers, and the nursing teams will all be aware of their allocation to the intervention group, since the method Palliative Reasoning will be implemented in daily care.
- The data collection will not be performed blindly. Firstly, the data are collected by local nurses who are aware of their allocation. Secondly, the research team who is involved in training the participants are also aware of the allocation, which is necessary to ensure an in-depth exploration of the experiences of the nursing team

during the up-following qualitative part of this study. This part will be described in a different research protocol, which is part of phase 4 of this study.

- Data analysis will be performed blinded. The researcher performing the data analysis will be blinded for the group allocation using labels. The labels will be opened after the analysis.

Randomization and allocation:

The clusters will be randomized through a simple randomization method with the Clinical Trial Randomization Tool from the National Cancer Institute(40,41). To minimize the risk of allocation bias, we will stratify between both homecare organization. The teams are informed about their allocation by the research team.

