4.2 Inclusion criteria

Patients are eligible if:

1. patient is 18 years or older.
2. The patient is diagnosed with a life limiting illness or frailty syndrome with a life expectancy of less than a year, estimated by the nursing team, based on the Surprise Question.
3. The patient lives at home.
4. The patient suffers from at least 1 symptom identified by means of the problem list of the Distress Thermometer.
5. The primary caregiver/informal caregiver is aged over 18 and able to speak and read Dutch.

A member of the nursing team is eligible if:

1. He/she working as a nurse assistant, registered nurse, specialized nurse, nurse practitioner or palliative care specialist consultant.
2. He/she is 18 years or older.
3. He/she works for at least 16 hours a week.

A nursing team of a participating homecare organizations is eligible if:

1. The nurses that are part of the nursing team are motivated to participate in the study.
2. The Nursing team has a total of ten or more patients under their care suffering from a life-limiting illness.

Chaplains, GPs, paramedics, social workers, and other healthcare professionals are eligible if:

1. He/she is 18 years or older.
2. He/she actively collaborates with one of the included nursing teams.

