5. METHODS

5.1 Study parameters/endpoints

5.1.1. Main study parameter/endpoint

The main study parameter is “perceived symptom control of patients and family caregivers dealing with a life-limiting illness, after one month of implementing the SMEtH-intervention”. Perceived symptom control is defined as the perception of symptom control by a patient, assessed at enrolment and after one month by a one item question: “Do you feel your symptoms are under control? Yes/ No?”. The endpoint of one month has been chosen to limit the number of missing data due to death of participating patients.

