5.4. Replacement of individual subjects after withdrawal

After the withdrawal of a patient, the patient will specifically be asked if the collected data up to that point may be used for the purposes of this study. If not, data regarding this patient will be removed from the database.

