6. STATISTICAL ANALYSIS

6.1. Primary study parameter(s)

To determine the effect of the SMEtH-intervention on the perceived symptom control after 1 month of patients of each nursing team, a mixed effects logistic regression analysis will be conducted. We will control for the following baseline measurements: age, gender, primary diagnosis, and performance status. Missing data are imputed using multiple imputation (MICE package in R) or if necessary, Bayesian imputation and analysis (Joint AI package in R). The quantitative data will be presented as odds ratio and 95% confidence interval (CI) in tables and graphs for the visualization of the results. Additionally, all analyses of primary and secondary study parameters are conducted by means of the statistical program RStudio, version 2022.12.0+353. (Vienna, Austria), and are considered statistically significant if $\alpha \leq 0.05$.

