6.2. Secondary study parameter(s)

Primary caregiver burden, symptom burden and quality of life of patients will be analyzed longitudinally using joint models for longitudinal analyses per symptom. Due to the fragility of the population, censoring of data will increase over time. Therefore, we will control for death, as well as age, gender, primary diagnosis, and performance status. Additionally, subgroup analyses for gender, age and primary diagnosis will be conducted for each secondary study parameter.

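### As written, section 5.2 removes enrolled patients whom a follow-up questionnaire shows to be symptom-free, and the plan does not say what happens to their data

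*Protocol*

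**What the plan says.** The patient paragraph of Protocol section 5.2 begins with the research team's baseline assessment. It continues: "Subsequently, patients will complete at one-, three- and six-months a questionnaire containing questions regarding symptom control, quality of life and symptom burden". The next sentence reads: "If these questionnaire reveals that a patient does not suffer from any symptoms, it will be excluded from the study". Excluded patients are then asked to fill in the Lastmeter, so that later symptoms can be picked up and the team is able "to be able to reconsider their inclusion in the study".

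Other parts of the plan that bear on this:

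- Section 4.2, patient criterion 4, already sets a symptom requirement at entry: "The patient suffers from at least 1 symptom identified by means of the problem list of the Distress Thermometer".
- Section 5.1.1 defines the primary outcome as a yes/no answer on whether symptoms are under control, "assessed at enrolment and after one month by a one item question".
- Section 5.4 has a data rule, but only for patients who withdraw and are asked whether their data may still be used: "If not, data regarding this patient will be removed from the database".
- Section 6.1 plans for missing values: "Missing data are imputed using multiple imputation (MICE package in R"), with a Bayesian alternative. It names no analysis population and does not mention excluded patients.
- Section 6.2, on the longitudinal secondary outcomes, says: "Therefore, we will control for death, as well as age, gender, primary diagnosis, and performance status". It makes no provision for exclusion because a patient is symptom-free.

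The document filed as the SAP is a data management plan. Its section 2.5 ticks that a missing-data policy exists but does not describe it.

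**The concern.** The exclusion sentence refers back to questionnaires, and those named immediately before it are the follow-up ones. A team following section 5.2 to the letter would take an enrolled patient out of the study at one month because the patient has no symptoms. That is exclusion after randomisation on a variable that the intervention is meant to change and that lies very close to the primary outcome. A symptom-free patient will usually say that symptoms are under control, so the rule would mainly remove successes.

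Two things are at stake. If excluded patients are left out of the primary analysis, the odds ratio can shrink or inflate, depending on how many successes each arm loses. If the one-month answer is kept, the primary endpoint is safe, but symptom burden and quality of life at three and six months are no longer collected from the patients who are doing best. Follow-up that was never collected cannot be recovered at the analysis stage. Nothing in the documents says that the caregiver's own follow-up stops.

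**Working it through.** **The plan's own figure.** Section 4.4 uses 30% vs 40%, 20 patients per cluster, 80% power and alpha 5% (taken as two-sided). With design effect 1 + 19 × ICC, pooled variance and a noncentral t distribution on 2(k − 1) degrees of freedom, all eight rows of Table 1 are reproduced, including the chosen 20 clusters per arm at ICC 0.001. The concern does not rest on an error in the sample size. Section 4.4 states no allowance for exclusions.

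**Inputs for the check.** From section 4.4: p = 0.30 (control) and 0.40 (intervention), 400 patients per arm, ICC 0.001 (design effect 1.019), and for comparison the highest ICC in Table 1, 0.02 (design effect 1.38). Assumed, because the documents give no symptom-free rate: the share s of one-month successes in each arm who are symptom-free and left out. It is also assumed that every symptom-free patient answers yes to the control question.

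**Formulas.**

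- Remaining patients: n = 400(1 − ps)
- Remaining success proportion: p(1 − s)/(1 − ps)
- Odds of success among those remaining: p(1 − s)/(1 − p), so the odds ratio is multiplied by (1 − sI)/(1 − sC)
- Power: normal approximation with unpooled variance, two-sided 5%, variance multiplied by the design effect

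**One case in full, 5% vs 10%.** The control arm loses 120 × 0.05 = 6 successes, leaving 114/394 = 28.9%. The intervention arm loses 160 × 0.10 = 16, leaving 144/384 = 37.5%. The odds ratio is (0.40/0.60)/(0.30/0.70) × 0.90/0.95 = 1.556 × 0.947 = 1.47. The standard error is √[1.019 × (0.289 × 0.711/394 + 0.375 × 0.625/384)] = 0.034, so the difference of 0.0857 is 2.52 standard errors and power is 71%.

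**Results** (shares removed, control vs intervention):

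| Shares removed | Patients removed | Remaining success | OR | Power, ICC 0.001 | Power, ICC 0.02 |
|---|---|---|---|---|---|
| none | 0 vs 0 | 30.0% vs 40.0% | 1.56 | 84% | 72% |
| 5% vs 10% | 6 vs 16 | 28.9% vs 37.5% | 1.47 | 71% | 58% |
| 20% vs 20% | 24 vs 32 | 25.5% vs 34.8% | 1.56 | 78% | 65% |
| 20% vs 40% | 24 vs 64 | 25.5% vs 28.6% | 1.17 | 15% | 12% |
| 20% vs 10% | 24 vs 16 | 25.5% vs 37.5% | 1.75 | 94% | 86% |

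The fall from 84% to 72% in the first row comes from the ICC and not from this rule. In the last row the higher power reflects an inflated odds ratio and is not a gain.

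If instead the same fraction f of each whole arm is symptom-free, then sC = f/0.30 and sI = f/0.40. At f = 5% the odds ratio is (0.35/0.60)/(0.25/0.70) = 1.63; at f = 15% it is (0.25/0.60)/(0.15/0.70) = 1.94. Equal removal across whole arms therefore also inflates the odds ratio.

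**The case against.** The strongest reply is that section 5.2 means a baseline check. The paragraph opens with baseline, the wording about reconsidering inclusion suits people not yet properly included, nurses do the first screening (section 7.2), and criterion 4 already requires a symptom. Removing patients at three or six months would also undercut the longitudinal analyses in section 6.2. The sentence is poorly drafted, so its position is weak evidence of intent. This may well be what the authors had in mind. It still has to be written down, because nothing limits the rule to baseline and staff could apply it at one month.

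Second, the one-month answer is in the same questionnaire that would trigger exclusion, so it would already be recorded, and no passage says it is deleted. That is correct. Harm to the primary endpoint needs the further step of leaving those patients out, and the plan neither requires nor rules that out. The loss of later follow-up does not depend on this step.

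Third, the shares are assumed and the largest are extreme. The introduction describes a population whose symptoms intensify towards death, so complete freedom from symptoms may be rare. With small shares the effect is small: 5% vs 5% leaves the odds ratio unchanged with power 83%, and 2% vs 4% gives 1.52 and 80%. This stands as a limit on size. The 20% vs 40% case shows how far the mechanism can reach and is not a forecast.

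Finally, the lack of a defined analysis population is a gap across the whole plan, and the data management plan (section 6) lists a separate analysis plan that was not among the documents. That is fair, but it does not settle how section 5.2 is to be applied.

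**Conclusion.** The concern holds, with medium confidence about intent. As written, section 5.2 excludes enrolled patients after randomisation for a state tied to the primary and secondary outcomes, and no passage says how their data are treated.

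The effect on the primary odds ratio arises only if excluded patients are left out of that analysis. Its size then depends on symptom-free rates that the documents do not give, and on the assumption that symptom-free patients answer yes. The odds ratio shrinks if more intervention successes are removed, which is plausible for a symptom intervention. It is unchanged, with lower power, if the shares are equal, and it inflates if fewer are removed. Removing as few as 6 vs 16 patients takes power below the planned 80%. If the one-month answer is kept, what remains is selective loss of later symptom-burden and quality-of-life data. The point should be settled before the rule is applied.

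**What to change.** In section 5.2, state that:

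- the no-symptom check is made once, at or before baseline, against inclusion criterion 4;
- no enrolled patient is removed because a later questionnaire shows no symptoms;
- Lastmeter re-screening applies only to patients found ineligible at that check, and their number is reported by arm. The counts matter because the check may come after cluster allocation is known. It would help to add from which date baseline and the one-month assessment run for a patient who qualifies later.

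In section 6, state that all other enrolled patients stay in follow-up and in the primary and secondary analyses by allocated cluster, including those symptom-free at one, three or six months.

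The cost is about three sentences in section 5.2 and one in section 6. No extra patients or visits are needed; symptom-free patients simply continue the planned questionnaires. If a baseline check was always intended, the change only records it.

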3. STUDY DESIGN

To determine the effect of the PR methodology, a pragmatic open-label multicenter cluster randomized controlled trial (cRCT) will be conducted in nursing teams working in primary care, from January 2024 to March 2026 in Utrecht, the Netherlands. We define a cluster as one nursing team in primary care, which is a group of registered nurses (RNs) and nurse assistants (NAs) collaborating within one home care organization and within the same district with support of specialized nurses (SN) and/or nurse practitioners (NPs). The trial consists of an intervention group and a control group. To enhance heterogeneity of usual care in the control groups and limit the risk of bias, randomization of the intervention will be conducted within one primary healthcare organization.

The intervention starts with the adequate identification of patients in need of palliative care by means of the surprise question “would I be surprised if this patient dies in the next year?”. If the answer to the question is “no”, the patient is suitable for receiving palliative care. After identification the PR methodology is followed by four phases. step 1: map out the individual situation, symptom burden and quality of life of the patient, step 2: summarize the current problems and develop a proactive policy plan, Step 3: evaluate the effect of the proactive policy plan on the symptom burden and quality of life of the patient, step 4: adjust the policy plan if necessary and continue evaluating. The Utrecht Symptom Diary – four dimensional (USD-4D) will be used to monitor the individual situation, symptom burden and quality of life of patients, as described in step 1. This is a Patient Reported Outcome Measure (PROM) and is validated in palliative care populations.

The nursing teams selected as control group will continue to provide usual care to patients with a life-limiting illness. We define usual care as “care that patients with a life-limiting illness, living at home, would be expected to receive as part of normal practice from that specific homecare organization”(29). To gain insight into normal practice of the control group, we will consult the organization’s current safety standards, guidelines, and protocols. Additionally, questions regarding normal practice will be asked during interviews with healthcare professionals.

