1.15 Last check date by datamanager

2023-07-25

1.16 Indicate which laws and regulations are applicable for the project (please check all that apply)

- Richtlijn Kwaliteitsborging Mensgebonden Onderzoek (Quality Assurance for Research Involving Human Subjects)
- Nederlandse gedragscode wetenschappelijke integriteit
- Gedragscode Gezondheidsonderzoek (Dutch)
- Wet op de Geneeskundige Behandelingsovereenkomst (WGBO) or Medical Treatments Contracts Act
- Algemene Verordening Gegevensbescherming (AVG) or General Data Protection Regulation (GDPR)

2. Data Collection

2.1 Give a short description of the research data.

| Subjects | Volume | Data Source | Data Capture Tool | File Type | Format |
|----------|--------|----------------------|-------------------------------|-------------------|--------|
| Human | 500 | EPD | Secured server, Julius Centre | Quantitative data | .csv |
| Human | 50 | Questionnaires | Castor | Quantitative data | .csv |
| Human | 100 | Voice recordings | Secured server, Julius Centre | Qualitative data | m4.a |
| Human | 100 | Transcripts | Secured server, Julius center | Qualitative data | .doc |
| Human | 25 | observations/reports | Secured server, Julius Center | Qualitative data | .doc |

2.2 Describe the flow of the data (name systems used and/or third parties, recipients) <add link to location where diagram is stored in RFS>

Nursing teams and the contact person working at Icare and AxionContinu select eligible patients --> nursing teams ask patients and their family caregiver to fill in the surveys --> surveys are handed out to the research team through the contact person of each nursing team --> research team store the data in Castor and analyse the data with R and/or SPSS.

Alongside the effect study a process evaluation will be carried out. This process evaluation is not mentioned in the study protocol of SMEtH, but has its own individual protocol. The flow of the data for the process evaluation part of this study is as follows: Zorgbelang Inclusief will guide the discussions with the focus groups --> observations are made by the research team during the focus groups --> observations focus groups are reported in Word.

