2.8 Which contracts are in place?

| Organization | Contract Type with UMCU | Role organization |
|-----------------------------------|-------------------------|--|
| AxionContinu | Consortium Agreement | Homecare organization where the intervention will be implemented and patients and family caregivers will be studied. |
| Zorgbelang Inclusief | Consortium Agreement | advisory and participatory role by guiding the conversation with the healthcare professionals as part of the process evaluation and by taking part in the development of end products. |
| Icare | Consortium Agreement | Homecare organization where the intervention will be implemented and patients and family caregivers will be studied. |
| ROC Midden Nederland | Consortium Agreement | advisory and participatory role by participating in guiding panels in to develop end products that are adapted to the education system |
| Hogeschool Utrecht | Consortium Agreement | advisory and participatory role by participating in guiding panels in to develop end products that are adapted to the education system |
| Integraal Kankercentrum Nederland | Consortium Agreement | advisory and participatory role by participating in the steering group and taking part in the development of end products. |
| | | |

2.9 State how ownership of the data and intellectual property rights (IPR) to the data will be managed

Data will be collected by researchers of the EPZU research team. In collecting Data the research team will not be collaborating with other parties.

Contact persons in each nursing team will be in contact with all individual participants. If the decision is made to use local researchers to collect data from participants instead of researchers of the EPZU, in light of the feasibility of the study, a contract will be drafted that fit the tasks and responsibilities of that specific context. Consequently, this DMP will be adjusted according to the latest amendments.

2.10 Use of new technology. Does your study involve the implementation of a technology that has not been used before at UMC Utrecht?

- No

2.12 Will the study need/use personal data (directly or indirectly identifying) from the Electronic Patient Files (EPD; HiX), DNA, body material, images or any other form of personal data?

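### The documents disagree on who collects the patient-reported outcomes, name no collector for the one-month primary item, and leave open a route through the treating nurses

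*Protocol*

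**What the plan says.** **Nurse route.** The blinding text in Protocol 5.2 says that "the data are collected by local nurses who are aware of their allocation". The SAP file is a data management plan (DMP). Its section 2.2 has the nursing teams ask patients and caregivers to complete the surveys, after which "surveys are handed out to the research team through the contact person of each nursing team".

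**Research-team route.** DMP 2.9 assigns data collection to the research team and adds: "In collecting Data the research team will not be collaborating with other parties". It also says that team contact persons will be in touch with every participant. Collection by local researchers is described as a possible later decision, which would need a contract and a revised DMP.

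**Baseline.** Protocol 5.2 says that "the research team will perform an assessment of baseline measurements in participating patients", and that this is "performed by post, mail, telephone, or teleconsulting depending on what is the most suitable" and least burdensome for the patient. The caregiver baseline is also given to the research team, with caregiver burden followed up by telephone.

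**Patient follow-up.** For one, three and six months, Protocol 5.2 says only that patients complete a questionnaire covering symptom control, quality of life and symptom burden. It names no collector and no mode.

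**Endpoint and blinding.** The primary endpoint (Protocol 5.1.1) is a single yes/no question on whether the patient feels the symptoms are under control, asked at enrolment and at one month. Patients, caregivers and nursing teams are not blinded. On the researchers, the blinding text says that "the research team who is involved in training the participants are also aware of the allocation". Only the analyst is blinded.

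**The concern.** Both routes stand in current text, so different teams could follow different ones, and the item that decides the trial has no assigned route.

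Under the nurse route the patient's answer passes through the team that provides the care. In the intervention arm that team has just had a four-day training and is being coached on the job in symptom management. The question asks, in effect, whether that care is working. A patient may be readier to answer Yes to such a team, or the team may prompt or explain the item differently. Control patients would also answer through their own team, so only the between-arm difference counts, but training and coaching give a reason to expect one. A bias that enters at collection is already in the data, so an analyst blinded by group labels cannot remove it.

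A second path runs the other way. The USD-4D is a secondary outcome in both arms (Protocol 5.1.2), and in the intervention (Protocol 3) it "will be used to monitor the individual situation, symptom burden and quality of life of patients, as described in step 1". If completed research forms pass through control teams, measurement could influence control care and reduce the contrast.

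**Working it through.** **Step 1. The passages side by side.**

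| Data | Protocol 5.2, procedures | Protocol 5.2, blinding | DMP 2.2 | DMP 2.9 |
|---|---|---|---|---|
| Patient baseline | Research team, remote modes | Local nurses | Through nursing team | Research team |
| Patient at 1 month (primary) | Not stated | Local nurses | Through nursing team | Research team |
| Patient at 3 and 6 months | Not stated | Local nurses | Through nursing team | Research team |
| Caregiver baseline | Research team | Local nurses | Through nursing team | Research team |
| Caregiver follow-up | Telephone, caller not named | Local nurses | Through nursing team | Research team |

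The blinding text, DMP 2.2 and DMP 2.9 speak of the data or surveys in general, so their entries apply to every row. At baseline the Protocol contradicts its own blinding text. For the one-month item its procedures text is silent, and the conflict is between the blinding text and DMP 2.2 on one side and DMP 2.9 on the other.

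**Step 2. The plan's own sample size.** Inputs (Protocol 4.4): 30% against 40%, 20 patients per cluster, ICC 0.001, alpha 5% (two-sided assumed, as sidedness is not stated), 80% power.

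- Design effect = 1 + 19 × 0.001 = 1.019.
- SE with pooled variance and 20 clusters (400 patients) per arm = √(2 × 0.35 × 0.65 × 1.019 / 400) = 0.0340.
- Noncentrality = 0.10 / 0.0340 = 2.94. With 2 × (20 − 1) = 38 degrees of freedom, the noncentral t gives power of 81.7%.
- With 19 clusters per arm (380 patients, 36 degrees of freedom) the same formula gives 79.6%, so 20 is the smallest number that reaches 80%. The planned figure reproduces.

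**Step 3. Illustration of a net differential shift.** Assume no true effect, 30% Yes, all 400 patients per arm responding, and a reporting shift *b* in the intervention arm over and above any shift in the control arm. The documents give no value for *b*.

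- SE = √(2 × 0.3 × 0.7 / 400 × (1 + 19 × ICC)) = 0.0327 at ICC 0.001 and 0.0381 at ICC 0.02, the ends of the range in Table 1.
- P(reject) = 1 − Φ(1.96 − b/SE) + Φ(−1.96 − b/SE).

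| Assumed *b* | ICC 0.001 | ICC 0.02 |
|---|---|---|
| 0 | 5% | 5% |
| 2 points | 9% | 8% |
| 3 points | 15% | 12% |
| 5 points | 33% | 26% |

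Using a pooled variance that allows for the shifted rate gives 9%, 15% and 32% at ICC 0.001, and 8%, 12% and 25% at ICC 0.02. A 3-point shift is 3/10 = 30% of the planned 10-point effect.

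**The case against.** **The lack of blinding is disclosed.** The trial is openly pragmatic and open-label, and the Protocol says that collection is not blinded. That stands: nothing is concealed. Disclosure does not settle which route applies, however, and it adds no safeguard.

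**The research team is unblinded too.** It knows the allocation and is involved in the training. A reader might infer that moving collection to it would blind the outcome. The documents do not support that. The move takes the treating nurse out of the patient's answer and no more. Patients know their allocation and report on themselves, so some response bias remains whoever collects.

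**Section 5.2 does not assign follow-up to the research team.** A reader might infer that it does, from the research-team role and remote modes given for baseline. The text covers baseline only. The general assignment comes from DMP 2.9, which itself leaves room for local researchers later.

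**Exposure of control teams to the USD-4D is not documented.** DMP 2.2 says how the surveys travel. It does not say that they are open, that anyone reads them, or that care changes as a result. Dilution is a possibility that nothing in the documents rules out, not an event they describe.

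**The error rates follow from the assumed shifts.** This is correct. The relevant quantity is the excess differential bias of the nurse route over collection by an unblinded research team, and the documents do not inform it. Any dilution would work in the opposite direction.

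**Nurse prompting may protect response.** The one-month endpoint was chosen to limit missing data due to death, so lower response would be a real cost. It has to be weighed, but nurses can remind patients without handling the answers.

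**Conclusion.** The contradiction is real and lies in current text. It extends to the primary endpoint, for which the Protocol's procedures name neither collector nor mode. Followed as written, the nurse route adds an avoidable source of differential response bias to a single subjective yes/no item, and blinded analysis cannot correct it. The plan should be changed.

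The size is unknown. The figures of 8-9%, 12-15% and 26-33% show how sensitive a 10-point comparison is to net shifts of 2, 3 and 5 points. They rest on those assumed shifts, 30% Yes, 400 responders per arm, ICC between 0.001 and 0.02, and a two-sided 5% test. They are not an estimate of this trial's error rate, and a reader should not infer that the trial has a false-positive rate of that order.

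**What to change.** 1. Reconcile Protocol 5.2 (procedures and blinding), DMP 2.2 and DMP 2.9. Name one collector and one mode, or one fixed order of modes, for each time point, identical in both arms.
2. Have the research questionnaires, at least the one-month primary item, completed by the patient and returned directly to the research team by post or electronically. Otherwise have them taken by telephone with a fixed script, where possible by a caller who is not told the allocation. The remote modes already planned for baseline suggest that this is feasible, so the statement that blinding is possible only at the analysis should be reconsidered.
3. State that treating teams neither handle nor see completed research forms. Use of the USD-4D as the intervention's own monitoring tool stays separate.
4. If post is used, add address to DMP 3.7, where that entry is now only a dash.
5. State as a limitation that response bias remains, because patients and the research team know the allocation.

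**Cost.** Much of this is wording. DMP 2.9 already gives collection to the research team, Protocol 7.2 provides for sharing patients' contact details with it, and DMP 3.7 lists name, telephone and e-mail. The added work is mailing and calling: up to 800 patient contacts for the one-month item, or 800 × 3 = 2,400 if all three follow-ups are covered, before deaths and not counting caregivers. Response may be somewhat lower without nurse prompting. Intervention patients may have to complete the USD-4D twice, once for care and once for research, which is a burden in a frail population.
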